- Pharmaceutical companies will be solicited through their patient assistance program for bulk supply of medications commonly prescribed to patients with kidney disease including antihypertensive, anti-lipid and antidiabetic drugs. These medications will be distributed by the DACC to the participating clinical centers for the use of study participants who need such assistance. We found this measure to be helpful in maintaining retention for other clinical studies.
- Participant reimbursement initially set at \$100 will be supplemented with an additional mileage reimbursement for participants traveling more than 100 miles to the clinical center for study visits.
- Per diem expenses for overnight accommodation will be provided to study participants whose travel calls for this, particularly during seasons of inclement weather.
- Participating clinical centers will be encouraged to offer evening and weekend appointments to make it possible for participants with work and other obligations that limit their flexibility to attend study visits during regular business hours (8:00 AM – 5:00 PM Monday-Friday).
- Mailing of appointment reminders, formal study participation anniversary greetings, newsletters and intermittent courtesy calls, courtesy visits to the participants during hospitalization and recognition of major life events are additional measures that will be undertaken to embrace study participants and hopefully retain their participation.
- Participants for whom relocation brings about a change of providers and an excessive travel burden for completion of study visits may continue in the study by completing phone call visits, on a case-by-case basis with permission from the DACC. In such instances, biological specimens and processing will be coordinated with a local laboratory and shipped directly to the NEPTUNE Biorepository.
- Discomfort that can result from study procedures will be rigorously minimized. For example, many of the participants may be on immunosuppressants with myelosuppressive adverse effect as part of the treatment for FSGS leading to high risk of anemia. Therefore, phlebotomy for study purposes will not withdraw more than 250 cc annually. Adult participants with hematocrit <28% will follow the pediatric volumes at that particular study visit (see Manual of Procedures for pediatric blood draw reductions). Participants with hematocrit <25% will have study phlebotomy waived for that particular study visit.

Retention of participants is central to the internal validity of the study and will be an extraordinarily high priority of the investigators and staff. A key element is a pleasant, attentive and responsive staff that provides a reasonably flexible visit schedule. Other clinical center features that promote high retention rates include local tracking systems; frequent staff meetings; free and convenient parking; personal contacts through birthday cards, holiday cards, sympathy cards and flowers; small gifts at visits; and modest monetary incentives.

There exist limited research data on participant retention in non-therapeutic clinical studies similar to the proposed cohort studies. Lack of therapeutic interventions may heighten the perception of no benefit in participation on the part of the study participant. The study team is acutely sensitive to this issue and would continue to evaluate new retention methods that can be tested and implemented in the cohort studies. The aggressive retention measures that are proposed herein will, in practice and in principle, always give way to the welfare of the study participants who are, first and foremost, patients. Respect, care and empathy for the circumstances of the participants will be the overriding consideration in all aspects of the recruitment and retention plan laid out by the proposing team.

4.C. Participant Withdrawal

It is anticipated that over the course of time, participants may withdraw from the study. This may occur officially by formal notification from the participant to the investigator, or unofficially when a participant cannot be reached via the usual methods of contact. Every effort will be made to acquire complete data on all participants.

As a longitudinal, observational study, missed study visits and unanticipated loss of contact are not deemed dangerous to the study participants.

Participants who relocate to an area from which it is no longer feasible to travel to the clinical center will be asked to permit study personnel to contact them annually for a telephone contact follow-up. Centers may offer inducements to participants who drop-out or relocate in the form of additional travel reimbursement in return for their continued participation. A participant relocating to an area close to a different NEPTUNE clinical center may transfer to that center.

4.D. Clinical Management of Participants

Investigators recognize the obligation and importance of reporting research information to the health care providers of participants. It is essential that investigators report clinically actionable information to the appropriate provider in a timely fashion. A procedure for reporting such information from participating reading centers to NEPTUNE investigators will be implemented and described in the Manual of Procedures.

4.E. Transmission of Study Findings and Response Time

An IRB approved summary of patient status including urine protein, kidney function and blood pressure control status is provided to the patient as a study “SnapShot.”

4.F. Clinical Alerts

Participants and their physicians will be notified as soon as possible if potentially serious medical problems are identified during any of the study visits although this is unlikely because study visits will typically coincide with routine clinic visits for most participants.

4.G. Referral for Clinical Care of Participants Lacking a Nephrologist

Every effort will be made to identify a primary treating nephrologist physician for each participant. In cases in which participants are unable to identify a primary nephrologist, the participant will be offered assistance in finding one. Each clinical center will establish a referral plan to accommodate participants with and without insurance. Clinical centers will develop a list of subsidized health centers for participants who are under- or uninsured and when necessary, clinical centers will direct the participant to social service agencies.

4.H. Standards of Care

Guidelines outlining current medical standards of clinical care are provided on the NEPTUNE study website as a resource for practicing clinicians. Participants will receive an explanation of these guidelines in conjunction with their test results. Participants will be encouraged to discuss results with their primary care physicians. Clinical center personnel and investigators will be accessible to answer additional questions.

4.I. Ethical Issues

4.I.1. Potential Risks to Participants

A minimal physical risk to participants arises from the diagnostic procedures for the collection of blood specimens, which require venipuncture of approximately 100 cc blood during the baseline visit and will require venipuncture of approximately 65 cc blood bi-annually in subsequent visits (see Table 2, page 26

for pediatric blood draw volumes). With venipuncture there is minimal risk of hematoma or infection. There is also a risk of dizziness/lightheadedness and rarely of fainting from blood draw.

A minimal physical risk of potential bleeding or injury to the kidney is added with the collection of an additional core of kidney biopsy tissue at the time of the diagnostic biopsy. This risk is considered small as the participant will be undergoing kidney biopsy for clinical indications. If the investigator/local physician collecting the kidney biopsy determines that the collection of an additional core of kidney tissue unduly increases the risk to the patient, this sample will not be collected. In these situations, residual kidney tissue from the clinical biopsy will be requested if available.

Risk/Benefit Assessment: While there is no immediate direct benefit to the individual participants of this study, there is considerable potential benefit to future patients and to society as a whole if molecular predictors of outcomes are identified. Identification of such predictors would potentially lead to interventions that may improve long-term outcomes for these diseases.

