In the first year, follow-up visits are expected to occur every four months after the baseline visit (see Appendices 8A and 8B, Visit Schedules), and subsequently every six months until the end of the study. Additionally, an unscheduled Relapse Visit can occur once annually per participant should a participant be scheduled to see their primary nephrologist giving an unscheduled visit window for each patient/year. In addition, the study protocol makes provision to include interval measures of renal function obtained for clinical purposes to be included in the study database.

3.C.2. Cohort A: Procedures During Screening/Eligibility [V_{SE}], Baseline [V1] and Biopsy [V_{BX}] Visits

General Principles: The Screening/Eligibility, Baseline, and Biopsy Visits period is expected to last at most 45 days around the time of renal biopsy. Before entering Baseline, participants will be screened to ensure that they meet the inclusion criteria and that none of the exclusion criteria are present. A de-identified screening log will be maintained in the study database.

Participants in the NEPTUNE cohorts will be followed for an initial period of up to 36 months or longer pending additional resources and depending on the date of enrollment. The following section describes the procedures to be implemented during the screening, baseline and follow-up phases of each cohort study.

3.C.2.a. Pre-screening

We will use a Forward Operating Study Subject (Participant) Awareness (FOSSA) System. The FOSSA System details that study personnel are trained to initiate screening at several points in the healthcare system where the opportunity exists to identify potential study participants. Study personnel screen medical records, appointment schedules and laboratory databases as consistent with local IRB protocols to identify patients who appear to meet inclusion/exclusion criteria.

3.C.2.a.(a) Screening/Eligibility [V_{SE}]

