- Fasting blood draw (Adult: 100 cc, pediatrics by weight according to Table 2, page 38) for the NEPTUNE Biorepository and central biochemical laboratory samples including lipid profile, glucose, total cholesterol and triglycerides. Blood volumes will be reduced in pediatric participants and in all participants, adult and pediatric, with a hematocrit below 28%.

If the baseline visit occurs on the same day as biopsy visit [V_{BX}], the blood draw will be deferred to a subsequent day, but not later than 45 days after the procedure. See Manual of Procedures for itemized list of baseline blood specimens to be drawn.

- Central biochemical laboratory 24-hour urine for Protein, Albumin, and Creatinine
- A "clean catch" research urine sample will be collected from all participants. Approximately 50 cc of the "clean catch" urine will be processed and transferred to the NEPTUNE Biorepository as outlined in the Manual of Procedures

Additionally, interim local laboratory results, between study visits, should be obtained from the participant's medical chart for:

- CBC [Hemoglobin, Hematocrit, WBC, MCV, MCH, MCHC, Platelets]
- Metabolic panel [Albumin, Bicarbonate, Total Bilirubin, Calcium, Carbon Dioxide, Chloride, Creatinine, Glucose, Alkaline Phosphatase, Potassium, Total Protein, Sodium, Aspartate Aminotransferase (AST), Alanine Aminotransferase (ALT), Magnesium, Phosphorus, Urea Nitrogen]
- Spot urine assay for Creatinine, Protein, Albumin, Protein:Creatinine Ratio

- 24-hour Urine Creatinine Clearance, Total Creatinine and Protein
- Urinalysis [Color, Appearance, Specific Gravity, pH, Leukocyte Esterase, Nitrite, Protein, Glucose, Ketones, Urobilin, Bilirubin, Blood, Sediment]
- Other laboratory results, as available from clinical records including: Cholesterol, Cystatin C, [C-Reactive Protein (CRP), Neutrophil Cytoplasmic Antibody (ANCA), Extractable Nuclear Antibodies (ENA), Nuclear Antibody Screen by Multiplexed Immunoassay (ANA), DNA Antibody Double-Stranded (Anti dsDNA), Cryoglobulins, Complements 3 and 4, Glomerular Basement Membrane Antibody (Anti-GBM), Anti Shiga-like Toxin (Anti-SLT)]
- Virology results as available from clinical records including: [Hepatitis B, Hepatitis C, Epstein Barr Viral Capsid Antigen, IgM (EBV), Cytomegalovirus Antibody: IgG and IgM (CMV), Human Immunodeficiency Virus: Proviral DNA by PCR Qualitative and Quantitative RNA Assay (HIV), Hantavirus, Parvovirus]

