At this visit, participants will also be administered the Patient Reported Outcome Measurement Information System (PROMIS) quality of life questionnaire and medication adherence questionnaire.

3.C.2.a.(c) Biopsy Visit [V_{BX}]

This visit is concurrent with the kidney biopsy procedure. Prior to the biopsy procedure, a 40 cc blood sample will be obtained for the NEPTUNE biorepository to provide pre-treatment samples of plasma, serum, and RNA profiles. A spot urine will also be collected pre-biopsy for storage in the study biorepository. If [V_{BX}] is concurrent with the first study contact, the urine sample will be used as the eligibility proteinuria measure. During the biopsy procedure, an additional renal core will be obtained for research purposes if and only if it has been confirmed that sufficient tissue is available for diagnostic purposes. The number of passes attempted for the clinical and research cores will not exceed 5 attempts. This tissue will be stored with the NEPTUNE study coordinator until it is confirmed that adequate tissue necessary for histologic diagnosis of renal disease has been received, processed, and the treating physician, in consultation with the renal pathologist, has determined there is no longer clinical need for this sample, at which time it will be released for research use in the NEPTUNE study.

Participants will be assigned to an initial study cohort (FSGS/MCD or MN) by the Pathology Review Committee.

3.C.2.a.(d) cNEPTUNE – Clinically indicated biopsy

Participants in the cNEPTUNE cohort who have a clinically indicated need for a biopsy will be consented specifically to obtain biopsy tissue for research, and will otherwise follow the procedures outlined above. cNEPTUNE participants receiving a kidney biopsy will continue to be followed in the cNEPTUNE cohort. These participants will be seen every 4 months following their clinically indicated biopsy for the first year, and then every 6 months thereafter.

Alternative Enrollment Schedule from Network Practices

At sites where networks of nephrology practices are utilized for recruitment, the Biopsy Visit, [V_{BX}], may be combined with [V_{SE}]. In this recruitment scenario consent must be obtained prior to securing renal tissue for the NEPTUNE Biorepository and Baseline Visit [V1] will occur at the time of [V_{BX}] or within 45 days of the procedure. As specified above, the baseline biobank blood draw cannot occur on the day of renal biopsy.

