Follow-up Visits [V2-V8] General Principles: The purposes for follow-up visits are to maximize participant retention; document the participant's clinical status including general well-being, the development of new symptoms or physical findings and course of the underlying disease; account for possible adverse events and side effects related to standard-of-care medication use; evaluate abnormal laboratory values; and identify participants who reach a study outcome.

If a visit or procedure is missed, the visit should be rescheduled as soon as possible within the allotted interval. An interval of \pm one month is targeted for all protocol visits.

If a visit or procedure is unable to be performed within the range of the study visit prior to the following visit's window, it will be documented as "missed". Study data that is able to be obtained (e.g., local labs, updates from the electronic medical record, etc), should be documented in the missed visit's case report forms.

Follow-up visits in year one will occur in person at four-month intervals (months 4, 8 and 12) after the Baseline Visit [V1]. Thereafter, follow-up visits [V5-9] will occur at six-month intervals through [V8], the 36-month follow-up. Subsequently, with the identification of additional funding, annual follow-up visits [V9-] will occur once per year. During the follow-up phase, participants will continue to be contacted by telephone as necessary between scheduled follow-up visits to update contact information, ascertain interim medical history and potential outcome events, and to assess health resource utilization. The V2- visits are to occur within a range of three months before and up to three months after the scheduled timeline according to the visit calendar.

The follow-up visits [V2-8] will include updates to the participant's medical history, concomitant medications, pregnancy history, a limited physical examination to include blood pressure, edema, and weight. Participants <21 years of age will also be measured for height. The follow-up visits [V9-] will be as inclusive of study data elements as possible, except in the case where these visits occur as either a phone call update or a chart data extraction.

The population respective Quality of Life questionnaires will be administered at each in-person study visit.

In addition, the following biospecimens will be collected at in-person visits:

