- Fasting blood draw (Adult: 65 cc – see Table 2 for pediatric blood volumes) for the NEPTUNE Biorepository and central biochemical laboratory studies.
- Spot urine for Creatinine, Protein, Albumin assay at Central biochemical laboratory.
- Central biochemical laboratory 24-hour urine for Protein, Albumin, and Creatinine.
- A "clean catch" research urine sample will be collected from all participants. Approximately 50 cc of the "clean catch" urine will be processed and transferred to the NEPTUNE Biorepository as outlined in the Manual of Procedures.

Local laboratory results from within \pm 90 days of the follow-up visit should be obtained from the participant's medical chart for:

- CBC [Hemoglobin, Hematocrit, WBC, MCV, MCH, MCHC, Platelets]
- Metabolic Panel [Albumin, Total Bilirubin, Calcium, Carbon Dioxide, Chloride, Creatinine, Glucose, Alkaline Phosphatase, Potassium, Total Protein, Sodium, Aspartate Aminotransferase (AST), Alanine Aminotransferase (ALT)], Magnesium (if available), Phosphorus (if available), Urea Nitrogen, and Cholesterol
- Spot urine assay for Creatinine, Protein, Albumin, Protein:Creatinine Ratio
- 24-hour Urine Creatinine Clearance, Total Creatinine and Protein
- Urinalysis [Color, Appearance, Specific Gravity, pH, Leukocyte Esterase, Nitrite, Protein, Glucose, Ketones, Urobilin, Bilirubin, Blood, Sediment]
- Virology results as available from clinical records including: [Hepatitis B, Hepatitis C, Epstein Barr Viral Capsid Antigen, IgM (EBV), Cytomegalovirus Antibody: IgG and IgM (CMV), Human Immunodeficiency Virus: Proviral DNA by PCR Qualitative and Quantitative RNA Assay (HIV), Hantavirus, Parvovirus]

The following updates will be performed at the follow-up visits that occur annually after the Biopsy Visit [V4, V6, V8]:

- Contact Information
- Demographics
- Family History
- Update healthcare providers (physician, practice and hospital)
- Update Permission to Obtain Medical Records
- NEPTUNE Contact Registry Information (if not previously offered)

3.D. Contact Schedule and Participant Procedures – Cohort B: cNEPTUNE

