- Virology results as available from clinical records including: [Hepatitis B, Hepatitis C, Epstein Barr Viral Capsid Antigen, IgM (EBV), Cytomegalovirus Antibody: IgG and IgM (CMV), Human Immunodeficiency Virus: Proviral DNA by PCR Qualitative and Quantitative RNA Assay (HIV), Hantavirus, Parvovirus]

At this visit, participants will also be administered the PROMIS and medication adherence Questionnaire, and enrolled into the SMS text messaging system. Parents will be asked to complete these questionnaires for pediatric subjects age 10 and under. Children and adult subjects will self-report for ages 8 years and greater.

3.D.1.a.(b) Follow-up Visits [V2-V9] per study calendar;

General Principles: The purposes for follow-up visits are to maximize participant retention; document the participant's clinical status including general well-being, the development of new symptoms or physical findings and course of the underlying disease; account for possible adverse events and side effects related to standard-of-care medication use; evaluate abnormal laboratory values; and identify participants who reach a study outcome.

If a visit or procedure is missed, the visit should be rescheduled as soon as possible within the allotted interval. An interval of \pm one month is targeted for all protocol visits.

If a visit or procedure is unable to be performed within the range of the study visit prior to the following visit's window, it will be documented as "missed". Study data that is able to be obtained (e.g., local labs, updates from the electronic medical record, etc), should be documented in the missed visit's case report forms.

Follow-up visits in year one will occur in person at 6 weeks, 4 months, and 12 months post enrollment. Thereafter, in-person follow-up visits will occur at six-month intervals through the 36-month follow-up. There is an additional phone visit at month 8. Additionally, an unscheduled Relapse Visit can occur once annually should a participant be scheduled to see their primary nephrologist.

During the follow-up phase, participants will continue to be contacted by telephone as necessary between scheduled follow-up visits to update contact information, ascertain interim medical history and potential outcome events, and to assess health resource utilization.

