who have not fully anticipated the effort needed to comply with the study protocol may drop out in their first year of enrollment as the study requirements overwhelm them. Therefore, we implement a “recruit-to-replace” strategy during the entire 30-month recruitment phase to ensure that early attrition does not jeopardize study power. A slightly higher rate of dropout is to be expected in the last two years of the study when many patients become “fatigued” from the protocol requirements, thus an initial recruit-to-replace will also ensure that the study has enough spend down to spare during the last two years of the study. Specific measures that will be taken to enhance retention include: (a) regular contact with referring physician practices; (b) use of trained, certified study personnel to perform study visits and; (c) meeting of investigator with each study participant at least once annually during one of the follow-up visits. Established practices such as mailings and personal telephone calls to remind patients about forthcoming appointments will also be incorporated. The study team will promptly provide results of study tests to referring physicians, pending additional funding. Participants will be encouraged to include family members in their follow-up visits since this may enhance the participant support without extra costs. Follow-up visit appointments will be scheduled with large appointment windows to allow for more flexibility and participants’ convenience.

The prevailing economic downturn coupled with the fact that many participants will be referred to the clinical centers from long distances, leads to an expectation that a significant proportion of the study participants will have fiscal limitations in meeting out-of-pocket travel expenses and in fact their prescribed medications. Studies in more economically advantaged populations also suggest that travel cost is an impediment to participation in clinical research when travel distance to/from the clinic is >100 miles. The NEPTUNE Steering Committee may vote to implement several measures to assist study participants:

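### Table 2 and the visit schedule exceed two blood-volume limits that the protocol itself states: 250 cc a year, and 30 ml per three months at 6-10 kg

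*Protocol*

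**What the plan says.** **Limits.** Section 4.B (Retention Plan) states that "phlebotomy for study purposes will not withdraw more than 250 cc annually", giving the risk of anemia under immunosuppression as the reason. The sentence sits in a list introduced by "The NEPTUNE Steering Committee may vote to implement several measures to assist study participants". Section 3.E.5 says child volumes are adjusted by weight to national guidelines, gives 30 ml per three months at 6-10 kg as the limit, and points to the blood-volume table.

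**Cohort A volumes and visits (3.C).** Before the biopsy, "a 40 cc blood sample will be obtained for the NEPTUNE biorepository". At baseline the entry is "Fasting blood draw (Adult: 100 cc, pediatrics by weight according to Table 2, page 38", and at follow-up it is "Fasting blood draw (Adult: 65 cc". On timing, "Follow-up visits in year one will occur in person at four-month intervals (months 4, 8 and 12" after V1. The baseline draw may not be taken on the day of the biopsy, so the two draws cannot be merged. In addition, "an unscheduled Relapse Visit can occur once annually per participant".

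**Cohort B visits (3.D.1).** "Follow-up visits in year one will occur in person at 6 weeks, 4 months, and 12 months post enrollment", with a telephone visit at month 8.

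**Table 2, children.** For under 20 lb, 21-51 lb and over 52 lb respectively:
- biopsy: 10, 20, 40 cc
- V1: 20, 50, 100 cc
- each follow-up: 20, 50, 65 cc
- relapse: 10, 20, 40 cc

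**Two other statements.** Footnote b of Appendix 8.A gives the biopsy draw as 10 cc. Section 4.I.1 describes about 100 cc at baseline and about 65 cc bi-annually afterwards.

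**The concern.** The limits and the table are both instructions to sites, and they cannot both be followed. A site that draws exactly what Table 2 and the calendar require will pass a stated participant-protection limit, for most larger participants through the routine schedule alone. The protocol gives no order of precedence and no rule for reducing or skipping a draw once a limit is near.

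At stake is participant protection and consistency between the schedule and the risk section. The statistical analysis is not touched.

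**Working it through.** **Method.** Add the scheduled draws over the visit calendar and compare the total with each limit. Weights are converted at 0.4536 kg per lb.

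**Can 250 cc be reproduced?** No. The closest compliant totals are 100 + 2 x 65 = 230 cc (V1 and two follow-ups, no biopsy draw) and 10 + 100 + 2 x 65 = 240 cc (the same with the 10 cc biopsy draw). Neither is the year-1 schedule.

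**Limit 1: 250 cc a year**

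| Participant and reading | Sum (cc) | Total | Against 250 |
|---|---|---|---|
| Cohort A adult or child over 52 lb, through month 12 | 40 + 100 + 3 x 65 | 335 | 34% over |
| Same, through month 8 | 40 + 100 + 2 x 65 | 270 | 8% over |
| Same, 10 cc biopsy draw, through month 12 | 10 + 100 + 3 x 65 | 305 | 22% over |
| Same, 10 cc biopsy draw, through month 8 | 10 + 100 + 2 x 65 | 240 | complies |
| Cohort B over 52 lb, no biopsy, through month 12 | 100 + 3 x 65 | 295 | 18% over |
| Same, without month 12 | 100 + 2 x 65 | 230 | complies |
| Same, without month 12, plus a relapse or biopsy draw | 230 + 40 | 270 | 8% over |

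An unscheduled relapse draw adds 40 cc to a Cohort A total, so 335 becomes 375.

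The 270 cc figure also survives a strict 365-day window. With the biopsy 45 days before V1, the window opening at the biopsy holds 40 + 100 + 65 + 65 = 270 cc.

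Children of 21-51 lb stay under the cap on the visits as written:
- Cohort A: 20 + 50 + 3 x 50 = 220 cc, or 240 cc with a relapse draw.
- Cohort B: 50 + 3 x 50 = 200 cc, or 240 cc with both a relapse and a biopsy draw.

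After year 1 an adult gives 2 x 65 = 130 cc a year, or 170 cc with a relapse draw, so the annual conflict is confined to year 1.

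**Limit 2: 30 ml per three months at 6-10 kg**

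- 6 kg = 13.2 lb and 10 kg = 22.05 lb, so the limit covers about 13-22 lb.
- Cohort B, about 13-20 lb: V1 + week 6 = 20 + 20 = 40 cc in 42 days. Week 6 + month 4 is again 40 cc, in about 80 days.
- Child of 21-22 lb (9.53-9.98 kg), either cohort: this weight falls in the 21-51 lb band, so V1 alone is 50 cc.
- Cohort A, under 20 lb: biopsy + V1 = 10 + 20 = 30 cc, exactly at the limit.

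**Section 4.I.1.** Read as twice a year, its wording gives 100 + 2 x 65 = 230 cc. The Cohort A schedule gives 335 cc. The difference of 105 cc is the biopsy draw (40) plus the third year-1 follow-up draw (65).

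**The case against.** **The cap may be optional.** Its list is one the Steering Committee may adopt, and neighbouring bullets also use firm wording, so the phrasing alone does not prove that the cap binds. This stands as a real ambiguity. It does not remove the conflict, because the sentence is a flat statement with its own safety reason. The 30 ml limit has no such lead-in.

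**Anemic participants are already protected.** A reader might infer that those at highest risk have no safeguard, and that would be wrong. At hematocrit below 28% volumes are reduced (4.B, Table 2 note, 3.E.5), and below 25% study phlebotomy is waived for that visit (4.B). These rules act on single visits. They enforce neither cumulative limit for anyone else.

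**Larger totals.** It is tempting to call 375 cc the scheduled volume, but the relapse visit is unscheduled; the schedule gives 335 cc. One can also build 270-290 cc at 21-51 lb and 400-440 cc over 52 lb for a Cohort B child biopsied at month 4. That requires the month-8 telephone visit to become an in-person visit with a draw. Sections 3.A.2 and 3.D.1 say biopsied children are seen every four months afterwards, but nowhere say that this visit converts, and the biopsy occurs only if clinically indicated. Those totals are not relied on here.

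**Section 4.I.1 is approximate.** It gives no annual total and fits six-monthly follow-up, which section 3.E.5 also describes. A reader might infer that participants are not told the true volume. The consent pages are not available, so that cannot be concluded. What remains is that 4.I.1 does not match the four-monthly year-1 schedule.

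**Conclusion.** The conflict is real, follows by addition from the protocol's own figures, and should be fixed.

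- **Annual cap, Cohort A adults and children over 52 lb:** 335 cc against 250 cc. With the 40 cc biopsy draw of section 3.C.2 and Table 2, the breach does not depend on month 12 (270 cc without it). With the 10 cc footnote it does (305 or 240 cc).
- **Annual cap, unbiopsied Cohort B children over 52 lb:** conditional. They reach 295 cc if month 12 belongs to year one, as section 3.D.1 places it; otherwise 230 cc, or 270 cc with a relapse or biopsy draw.
- **Pediatric limit:** 40 cc by week 6 for Cohort B at about 13-20 lb, and 50 cc in one V1 draw at 21-22 lb in either cohort, against 30 ml. This needs no assumption about month 12, relapse or biopsy. The protocol gives no count of children in this narrow weight range and states no limit below 6 kg.

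The sums assume that every draw is taken in full and that no hematocrit reduction applies. No endpoint, power figure or analysis changes.

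**What to change.** 1. State that 250 cc per 12 months and 30 ml per three months (6-10 kg) prevail over Table 2. A draw is reduced or skipped once a limit would be passed, counting biopsy, relapse and post-biopsy draws.
2. Move the lowest weight-band boundary in Table 2 to 22 lb (10 kg), and set that band's volumes so that all draws in any three months total at most 30 cc. The clinical team should choose the volumes.
3. Align section 4.I.1 and Appendix 8.A footnote b with the resulting schedule, including the biopsy draw and all three year-1 follow-up draws.

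Do not resolve the conflict by raising the cap for children. A cap set to the largest constructed total, 440 cc, would let a child just over 52 lb give more than an adult's 375 cc.

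**Cost.** Protocol wording and a revised Table 2. Year-1 biorepository blood falls by about 335 - 250 = 85 cc per Cohort A adult, or 375 - 250 = 125 cc if a relapse draw occurs. Section 3.E.5 treats baseline blood as the scarce resource, so the reduction is better taken from follow-up. Keeping 40 + 100 cc leaves 250 - 140 = 110 cc for three follow-up draws, about 36 cc each when there is no relapse draw.
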